Screening visit 2 ([name]-CHBR Suite; ~ 1 hour): The second laboratory screening visit will consist of a mock fMRI scan to improve data quality and ensure

participants are eligible and willing to complete the fMRI measurement. Participants will fill our clincard forms and receive clincard.

Baseline Measurement 1, Diet Period 1 (229 Wallace Hall; ~1-1.5 hours): If participants are eligible and willing they will come in and undergo measurement of body composition (BIA), hip and waist measurements, and executive function.

Baseline Measurement 2, diet Period 2 ([name]-Human Neuroimaging Lab; ~2 hours): The second baseline measurement will consist of participants undergoing fMRI tasks with a dairy based milkshake and an abdominal fMRI. Participants will also complete a computerized Delay Discounting measure. Participants will then be randomly assigned to their first diet condition.

Two-week diet period 1 (12 daily visits [Mon-Sat], 334 Wallace Hall; ~30 min/day, 6 hours total): Following the eligibility screening and baseline measurements, participants will come into the lab each morning in the fasted state, be weighed (to insure weight stability), eat their breakfast in the dining laboratory, and be provided with a cooler of remaining food for the day. On the first Saturday of diet, participants will receive the Actigraph and have them until Thursday, when they should return it.. During the second week of the diet, the following measurements will be made: On day 13, executive functioning, body composition (BIA), and waist and hip measurements will be assessed. On day 14, meal palatability will be assessed using the LHS after their supervised breakfast meal, then they will travel to Roanoke for fMRI measurements.

Optional component: Participants may provide a 24-hour urine sample during this diet period, if they are willing to do so.

Day 14 fMRI 1 ([name]-Human Neuroimaging Lab; ~3 hours): After meal palatability assessment, the participant will travel to Roanoke to undergo fMRI with a dairy based milkshake after diet period to assess changes in brain response after exposure to the diet condition. Abdominal fMRI will be repeated to assess changes in subcutaneous, visceral, and liver fat. Computerized delay discounting task will be repeated after the diet period to assess any changes in discount rate. fMRI assessments will be performed ~ 3 hours after the supervised breakfast meal.

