Ad libitum Buffet Meal: (334 Wallace Hall; ~ 1 hour): On day 15, the participant will rate internal state, engage in an ad libitum energy intake and food selection assessment. Visual Analog Scales (VAS) will be completed at time 0 (baseline) and time 30 (30 minutes after exposure to the buffet meal). Time spent eating will be covertly recorded (meal start/stop time). Kcal and grams of food consumed will be covertly recorded, to calculate meal eating rate (g/min, kcal/min). Foods selected will also be covertly recorded. Eating in the absence of hunger will be assessed immediately after the buffet meal. Four snacks items will be provided and participants will be asked to take a bite of each one and rate its palatability using the LHS, and then be left alone to eat the remainder of the snacks or look at the magazines while they wait for the next part of the study. Participants will be left to consume the snacks or relax for 15 minutes.

22-253 Influence of ultra-processed foods on reward processing and energy intake

Eating in the Absence of Hunger Measurement (Take Home): Participants will be given a box of snacks to assess eating in the absence of hunger outside the laboratory environment. Snack boxes will be returned to study staff the next morning. Staff will document the amount and type of snacks consumed.

4 week washout period: Participants will be asked to resume their usual diet. In the final week of the washout (week 4), assessments of dietary intake, PA, EF, and fMRI will be completed in two baseline visits for the second feeding period (listed below). These will serve as the baseline assessments for the second feeding period. For females, washout duration may be extended to 6 weeks if needed, in order to schedule EF, fMRI, and ad libitum buffet meal post- testing in the same menstrual cycle phase.

Baseline Measurement 1, Diet Period 2 (229 Wallace Hall; ~1-1.5 hours): Participants will undergo executive function, BIA with hip and waist measurements,

Baseline Measurement 2, diet Period 2 ([name]-Human Neuroimaging Lab; ~3 hours): The second baseline measurement will consist of participants undergoing fMRI tasks with a dairy based milkshake. Abdominal fMRI will be completed to assess changes in subcutaneous, visceral, and liver fat. Computerized delay discounting task will be completed.

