Participants will then undergo Feeding Period 2, following the same procedures used in feeding period 1. A BIA with hip and waist measurements will be performed on day 13, when the EF measures are completed.

Optional component: Participants may provide a 24-hour urine sample during this diet period, if they are willing to do so.

The total number of visits will be ~34; the exact number of visits may vary slightly due to scheduling of research staff and participants. Total number of hours for participants will be ~33-35.

Schedule of Study Activities/Assessments: Young Adults Eating Habits

Procedures	Eligibility Pre-Screening	In-Person Screening		Baseline Measures 1 (wk prior to diet)		14-d Diet Period 1 (12 visits*)		4-wk Washout **	Baseline Measures 2**		14-d Diet Period 2 (12 visits*)	
		Day 1	Day 2	Day 1	Day 2	Wk 1	Wk 2		Day 1	Day 2	Wk 1	Wk 2
Pre-Screening Survey QuestionPro	x											
ICD sent via email	x											
ICD reviewed, signed		x										
Health History Form Mens, cycle calendar (paper form)		x										
mYFAS		x										
TFEQ		x										
Life Events Checklist		X										
IPAQ (short)		X										
24-hr diet recall *2 nd & 3 rd via phone		x										
Height, Weight		x										
Weight (daily during diet periods) Start diet-Fridays (women: early follicular phase)		x		x		X d. 1 Fri	x		x		x	
Mock fMRI scan (Roanoke)			x									
Assigned to Diet Condition (sequence) Roanoke mock fMRI			x									
ClinCard (fMRI visits) Roanoke			x				x				x	
BIA with Waist:Hip ratio				X M/T/W		X d. 13 Wed		X M/T/W			x d. 13 Wed	
Executive Function				X M/T/W		X d. 13 Wed		X M/T/W			X d. 13 Wed	
PA (4 d. Actigraph)					X Sa-Th					X Sa-Th		
fMRI with milkshake, 3 hrs post-bfast*** with Liver Fat Roanoke				X Th		x d. 14 Th		X Th			X d. 14 Th	
DD task Roanoke				X Th		x d. 14 Th		X Th			X d. 14 Th	
Ad Lib Buffet Meal with VAS at min 0 & 30						X d. 15 Fri					X d. 15 Fri	
EIAH (lab), w/ LHS (15 min)						X d. 15 Fri					X d. 15 Fri	
EIAH (home) Snackbox, LHS, VAS Return Saturday (& pay via ClinCard)						X d. 15 Fri					X d. 15 Fri	
DeBrief & Final Report to Participant											x	

*During the controlled diet periods, participants will come to the Dining Lab daily for breakfast Monday-Saturday. On Sat, they will receive food for Sunday. Body weight will be measured at each visit to insure weight stability.

22-253 Influence of ultra-processed foods on reward processing and energy intake

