Tech (VT IRB). All serious AEs will be reported by the PI within 48 hours of occurrence to the VT IRB. Safety reports will be sent to the MPI and MD safety officer. The MPI will be responsible for assembling the data and producing these reports as well as assuring that all parties obtain copies of these reports. Reports will be submitted annually to the VT IRB for review. The frequency of data review for this study differs according to the type of data, the availability of data collected, and the perceived level of risk. Participants will be queried at each laboratory visit when meals are picked up as to any side effects or changes in health status that they experience, over the two 2-week controlled feeding interventions.

Any reported side effects will be discussed immediately with the MPI and the safety officer. The safety officer will determine if medical intervention or other actions are warranted. Participants will be referred to their primary care physicians if there are incidental findings.

Data type	Frequency of reviewing reports
Subject accrual (adherence to the protocol regarding demographics, inclusion/exclusion)	Semi-annually
Adverse event rates	Semi-annually
Compliance to treatment	Semi-annually
Out of range laboratory data	Semi-annually
Stopping rules report regarding statistical power implications of drop outs and missing data	Semi-annually
Side effects of controlled diet, study procedures	Daily, when meals are picked up

17.3 If applicable, indicate which procedures might have risks to the subjects that are currently unforeseeable. This will be rare, and usually applicable when testing a new drug or device or a new use of an existing drug or device:

N/A

17.4 If applicable, indicate which procedures might have risks to an embryo or fetus should the subject be or become pregnant:

17.5 If applicable, describe risks to others who are not subjects (e.g., collection of sensitive health data that might affect sexual partners if disclosed, mandatory reporting of abuse, DNA testing that might affect family members or relationships):

N/A

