21.0 Provisions to Monitor the Data to Ensure the Safety of Subjects

Safety monitoring is required when research involves greater than minimal risk and is sometimes appropriate for other studies.

21.1 Describe:

- *The plan to periodically evaluate the data collected regarding both harms and benefits to determine whether subjects remain safe (e.g., periodic reporting to the IRB, establishing a data monitoring committee, reporting data monitoring committee findings to the IRB and the sponsor).*
- *What data you will review, including safety data, unexpected events, and data that show the ability to produce the intended results.*
- *How the safety information will be collected (e.g., with case report forms, at study visits, by telephone calls with subjects).*
- *The frequency of data collection, including when safety data collection starts.*
- *Who will review the safety data and with what frequency.*
- *The statistical tests for analyzing the safety data to determine whether harm is occurring.*
- *Any conditions that will trigger an immediate suspension of the research (e.g., a serious adverse event).*

The data safety monitoring plan (DSMP) for this study focuses on close monitoring by the multiple principal investigators (MPI) and study medical director, along with prompt reporting of excessive adverse events and any serious adverse events (AEs) to the NIH and to the IRB at Virginia Tech (VT IRB). All serious AEs will be reported by the MPI within 48 hours of occurrence to the VT IRB.

Safety reports will be sent to the MPI and study MD. The Project Coordinator will be responsible for assembling the data and producing these reports as well as assuring that all parties obtain copies of these reports. Reports will be submitted annually to the VT IRB for review.

The frequency of data review for this study differs according to the type of data, the availability of data collected, and the perceived level of risk (see table below). Participants will be queried at each laboratory visit when meals are picked up as to any

side effects or changes in health status that they experience, over the two, 2-week controlled feeding periods.

Data type	Frequency of reviewing reports
Subject accrual (adherence to the protocol regarding demographics, inclusion/exclusion)	Semi-annually
Adverse event rates	Semi-annually
Compliance to dietary treatment	Semi-annually
Stopping rules report regarding statistical power implications of drop outs and missing data	Semi-annually

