Side effects of controlled diet, study procedures	Daily, when meals are picked up

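### The last written side-effect query of each feeding period comes before the day-14 scan and the final study foods, so these exposures have no prompt query after them

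*Combined protocol and SAP*

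**What the plan says.** Section 17.2 states when participants are asked about side effects: "Participants will be queried at each laboratory visit when meals are picked up as to any side effects or changes in health status". The same sentence confines the question to the two feeding periods. Section 21.1 repeats the rule in nearly the same words. Both sections carry a review table with a row headed "Side effects of controlled diet, study procedures", reviewed daily at meal pick-up. The query is therefore meant to cover procedures as well as food. Adverse event rates are reviewed semi-annually.

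Section 8.2 fixes the calendar. Breakfast visits run Monday to Saturday, 12 per period, and "On Sat, they will receive food for Sunday". On day 14, "fMRI assessments will be performed ~ 3 hours after the supervised breakfast meal". The buffet, the in-lab snacks and the handover of the snack box follow on day 15. Then "Snack boxes will be returned to study staff the next morning". No side-effect question is written for day 15, the box return or the Baseline 2 visits.

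**The concern.** A query can only pick up what happened before it was asked. Here it is attached to an event, the meal pick-up, that stops before the exposures of each period are over. Section 17.1 names unknown food allergy, food-borne illness and MRI effects as the foreseeable risks. The last study foods and the post-diet scan carry those risks, yet they fall after the last pick-up.

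If staff follow the text exactly, the semi-annual adverse event rates will miss events from the end of each diet unless a participant volunteers them. In a crossover there is a second cost: an event late in period 1 or during the washout is not systematically recorded before period 2 starts.

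**Working it through.** **Inputs, all from section 8.2 and its schedule.** Diets start on a Friday. Pick-ups are Monday to Saturday, 12 per period. Day 13 is Wednesday, day 14 Thursday and day 15 Friday. Baseline scans are on the Thursday before the diet. The snack box comes back on Saturday. A scan may be repeated 2-5 days later. Washout is 4 weeks, extendable to 6 for females.

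**Step 1: reproduce the 12 visits.** With day 1 a Friday, the Sundays are days 3 and 10, and 14 - 2 = 12. The query days are 1, 2, 4-9 and 11-14. This matches the stated 12, and days 13, 14 and 15 fall on the stated weekdays.

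**Step 2: find the next query after the last one of period 1.** The last is at breakfast on day 14.
- 4-week washout: period 2 starts on day 14 + 28 + 1 = 43, a Friday. The gap is 43 - 14 = 29 days.
- 6-week washout: period 2 starts on day 14 + 42 + 1 = 57, a Friday. The gap is 57 - 14 = 43 days.
- After period 2 no further query is written.

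**Step 3: set each exposure against the next written query.**

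| Exposure | When | Next written query |
|---|---|---|
| Baseline scans (2) | Thursday before day 1 | Day 1, normally the next day |
| Foods eaten between the day-1 and day-14 queries | Days 1-14 | 24 h apart, or 48 h Saturday to Monday |
| Post-diet scans (2) | Day 14, about 3 h after breakfast | 29-43 days later (period 1); none (period 2) |
| Repeat of a post-diet scan | Days 16-19 (14 + 2 to 14 + 5) | No prompt query; none after period 2 |
| Rest of the day-14 food | Day 14 | As for the post-diet scans |
| Buffet and in-lab snacks | Day 15 | As above, one day less for period 1 |
| Take-home snack box | Days 15-16 | As above; no prompt query |

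**Step 4: look at the visits that already exist.** Staff see the participant on day 15, on day 16 (box return) and at two Baseline 2 visits. With a 4-week washout, the Baseline 2 visits fall on days 39-41 (Monday to Wednesday) and day 42 (Thursday). Asking the question at these visits cuts the wait after the day-14 query from 29-43 days to 1 day. It also puts a query one morning after the snack box is handed out, in both periods.

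**The case against.** The strongest reply is that MRI effects arise in the scanner and are handled there. Section 17 provides an intercom, a squeeze bulb and a reassessment of comfort, and participants with unusual sensations or nerve stimulation are withdrawn. For acute scanner effects this stands. It does not reach anything noticed after the participant leaves, and it has no bearing on food.

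It can also be said that the study is described as minimal risk and has no safety endpoints, that no efficacy conclusion rests on these rates, that participants may volunteer events, and that a manual of procedures is planned and may fill the gap. All of this limits the importance of the point. It does not change what the two sections instruct. The day-15 ratings do not substitute for the query, because they concern hunger, fullness and liking. Treating day 15 as a pick-up because a snack box is handed over would still leave that box without a query after it.

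Two stronger readings are tempting, and the documents support neither.

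- **All four scans lack a later query.** Both baseline scans fall on a Thursday and are normally followed by the day-1 query on Friday, whose stated scope includes procedures. The right count is two of four. The feeding-period wording leaves it slightly unclear whether an event on the baseline scan day is in scope, but the point does not depend on that.
- **The 48-hour rule for serious events is unworkable.** Section 17.2 says "All serious AEs will be reported by the PI within 48 hours of occurrence to the VT IRB", and section 21.1 says "All serious AEs will be reported by the MPI within 48 hours of occurrence to the VT IRB". A reader might infer that the clock often expires before staff can know. During feeding, successive queries are never more than 48 hours apart, although an event just after a Saturday visit leaves almost no time to report. Outside feeding, spontaneous reports are not excluded. Counting from occurrence is also the stricter convention, and the documents do not show what the IRB requires. This is a matter to confirm, not an error.

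**Conclusion.** The point holds for the end of each feeding period. Two of the four scans, any repeat of them, and the last study foods have no prompt written query. The wait is 29-43 days from the day-14 query after period 1, and there is no later query after period 2. The effect is incomplete adverse event rates for late exposures. It does not bias the primary or secondary endpoints, and the study remains low risk. The change is worth making because it is nearly free.

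This rests on four assumptions: diets start on Fridays and scans fall on Thursdays as scheduled; food for the rest of day 14 is supplied at that day's breakfast visit; the written rule is followed as it stands; and nothing is volunteered between visits.

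**What to change.** In sections 17.2 and 21.1, keep the query at meal pick-ups and extend it to the day-15 buffet visit, the snack-box return, any repeat-scan visit and both Baseline 2 visits. Word it to ask about the whole interval since the last query, so that Baseline 2 collects late period-1 and washout events before period 2 begins. Change the matching row of both review tables so that it no longer refers to meal pick-up alone.

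The cost is wording in two sections and one existing question at visits that already take place. A few more minor events will be recorded. One limit remains: unless there is a repeat scan, the box return is the last contact of period 2, so anything that starts after it would still depend on a spontaneous report.

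Separately, ask the sponsor to confirm against its IRB policy whether the 48 hours for serious events run from occurrence or from staff awareness. No change to that clock is proposed here.

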18.0 Potential Benefits to Subjects

18.1 Describe the potential benefits that individual subjects might experience from participating in the research. Include the probability, magnitude, and duration of the potential benefits, as this will be useful to the IRB's risk:benefit analysis. Do not include benefits to society or others. Do not list monetary or non-monetary compensation for participation, as this is not a benefit. These should be included in section 2 or 3 of this document:

The study does not have any potential benefits to participants. However, it may contribute to participants' knowledge regarding their health.

18.2 If applicable, specify that there are no anticipated direct benefits for participants:

There are no anticipated direct benefits to participants.

19.0 Data Management and Confidentiality

19.1 Describe procedures that you will use for quality control to ensure validity of collected data:

Nutrient composition of the controlled diets will be verified using food ingredient labels and standard food composition tables.

A detailed Manual of Procedures (MOP) will be developed, to improve intervention fidelity and replicability. All study staff will be trained in study procedures prior to implementation. The project director will conduct random audits of foods provided to participants to verify accuracy of controlled diet provision.

All data will be collected and analyzed by trained research personnel. They will be trained via MRI safety training, Human Subjects Protections, and vigorous training in standard laboratory procedures (perceptual testing, etc.)

19.2 Describe any existing data or biospecimens you will obtain as part of this study. Include:

- *Variables or samples to be obtained*
- *Source of the data or specimens*
- *Your authorization to access or receive the data or biospecimens*
- *Whether the data or biospecimens are publicly available*
- *Whether the data or specimens you receive will contain identifiers*

N/A

19.3 Describe the steps that you will take to handle and secure study data during data collection, storage, use, and transmission. Include information about training of study staff, authorization of access, password protection, encryption, physical controls, certificates of confidentiality, separation of identifiers and data, etc.:

Data will be coded using a 6 character number. Participant IDs will be created sequentially starting at YAEH01. The key linking the participant name or identifiable information and the code will be stored on an encrypted server managed by the FBRI and HNFE IT department. This server can only be accessed by those on the research team. All study data will be kept on a separate server from identifiable information, also encrypted. Any paper documents generated that contain other identifiers, such as name, phone number, or email will be stored in a locked file cabinet accessible only by authorized staff. De-identifiedIdentifiable participant information will be kept indefinitely or at the written request of the participant. De-identified data may be shared with others outside of the research team without reconsent.

Dietary recall data will be recorded using a standardized 24-hour recall form. Forms will be stored in a locked cabinet in Wallace Hall. Data will be analyzed using NDS-R on the password-protected desktop computer located in PI [name]'s locked laboratory in Wallace Hall (rm 334).

Per Virginia Tech policy, in order to compensate participants, social security number (or Taxpayer ID) and street address will be collected via a W-9 form or W-8BEN. The participant address and SSN will be entered into the ClinCard systems, which is a HIPAA compliant payment system approved by Virginia Tech. After entry, this form will be given to and stored by the central administration at the FBRI to be used if it is required that a tax statement be sent to the participant, based on Federal Income Tax regulations. Study staff will not store any documents with SSN or address used for payment purposes.

19.4 For multi-site studies, describe how data or specimens will be handled and secured for each site (e.g., central or disseminated data storage, data coordinating center):

N/A

19.5 Describe the plan for data disposition following the conclusion of the study (e.g., long term maintenance of data, data destruction methods).

- *What information will be included in the long term storage of data or specimens?*
- *How long will the data or specimens be stored?*
- *Where and how data or specimens will be stored?*
- *Who will have access to the data or specimens during long term storage?*
- *Who is responsible for receipt or transmission of the data or specimens?*
- *How will data or specimens be shared or transported?*
- *When and how will personal identifiers be destroyed?*

All study data will be stored on the PI's, password-protected laboratory computer and secured servers (FBRI and HNFE) until at least 5 years after the last publication or presentation. All participant study data will remain de-identified and stored in code format.

